7.2.2 OTHER ASSAYS OR PROCEDURES

None.

7.3 STUDY SCHEDULE

7.3.1 SCREENING

Visit 1, Day -1 (Skin Types I-III) or Day -5 (Skin Type IV)

Point of enrollment

Point of enrollment is defined as the point where the patient, after having signed the informed consent form, is confirmed to fulfill all criteria for eligibility.

Following the point of enrollment, each subject will receive study treatment and study questionnaires.

Screening Visit

If the subject meets the preliminary study criteria, the study doctor, and/or his/her designee, will obtain an informed consent from the subject prior to any study procedure, clearly indicating his/her understanding of the requirements and possible risks associated with study participation and other applicable treatment options.

During the first visit, the study investigator, and/or his/her designee, will screen the subject for eligibility to participate in the clinical study using the inclusion/exclusion criteria. A urine sample for the pregnancy test will be obtained (in patients of child-bearing potential). During screening, the study doctor will review the subject's medical/surgical history and examine the subject's targeted area to ensure that it meets the study criteria. The subject will complete screening and the treatment will be scheduled.

During the first visit, the investigator will ask women of child-bearing potential for the date of their last period, if not applicable the investigator shall inquire about the form of contraceptive they use to confirm they meet the inclusion criteria.

Test Spots

A small test spot will be performed in a non-conspicuous area of the treatment site, prior to the first complete session. Test spots are performed to establish the following requirements:

- Confirm the patient's suitability for treatment: For skin types I-III wait 24-48 hours before assessing the skin response and 5-7 days for skin type IV.

- Establish and confirm treatment parameters: If the desired endpoint of erythema and edema – in a tip-shaped pattern – has not been achieved within 10-15 minutes, increase the RF indicator level and perform another test spot. If the response is excessive, decrease the parameters and perform another test spot.

Test spot results will indicate if the patient can tolerate the treatment without developing adverse effects. According to patient tolerance to the test spot, you may determine treatment parameters and whether anesthesia is needed. In addition, it is advisable to perform a test spot whenever changing parameters.

Treatment

Shave any hair in the treatment area. Ensure that the skin is completely dry during the entire treatment. If the skin moistens during treatment (i.e. perspiration, etc.) re-wipe the skin with an alcohol pad and ensure that the skin is completely dry before continuing the treatment.

Set the treatment parameters (Voltage 240-280, 15-20 ms pulse duration). Set the desired energy level according to the skin type, severity of the treated condition, treatment area, bone proximity, etc. Set conservative parameters from a test spot for the first treatment, and then gradually increase during treatment or in subsequent treatments according to the desired impact and test spot results.

Select the desired tip pattern to Full or Half if the tip extends beyond the boundary of the scar tissue in order to restrict treatment to the scar tissue. Treatment consists of a single pass over the treatment area, however, the test spot will consist of a single pulse. Adjust the treatment parameters according to the test spot response. To perform the treatment, place the tip on the target zone, perpendicular to the skin surface and with full contact with the skin. Emit a pulse by pressing the applicator's trigger; this will create a tip-shaped pattern on the patient's skin that will appear 1-2 minutes later. Move the applicator to an adjacent spot on the skin overlapping by 10% and emit another pulse (not applicable to the test spot). There should be no untreated gaps between the pulses.

Examine the treated area. The immediate responses, indicative of the desired effect, are erythema and edema in the immediate area of the tip-shaped pattern and possibly also around it. The edema usually appears 1-2 minutes after pulsing and reaches its peak (of up to moderate edema) within 30 minutes. It should be noted that erythema is not easily noticeable – if at all – in darker skin types. Therefore, the edema will be more prominent in these patients. After completing a full pass on the entire treatment area, if untreated patches of skin are apparent, re-treat these patches as per the following procedure:

- Wipe the untreated patch of skin with a dry gauze pad.
- Treat the untreated patches of skin as normally.

Fine-tuning of the parameters should be done before proceeding to treatment of the entire sub-area with the selected parameters. Treatment consists of a single pass over the designated area. The applicator tip should be placed on the skin, a pulse emitted, then lifted and moved to an adjacent spot of the skin. The emitted pulses should create tip-shaped patterns. Leave, no untreated gaps between the pattern marks, while also being careful not to overlap the treated zones. The parameters can be modified during subsequent visits, as per the practitioner's discretion.

Post-Treatment Care

Post-treatment cooling is not necessary. In the event of post-treatment discomfort, it is recommended to cool the treated area immediately with air cooling. Cold (not frozen) packs may also be used.

Blistered or ulcerated skin can be treated with a prescribed cream. Tiny scabs of less than 1 mm diameter will usually form 24-72 hours post-treatment and may remain for several days. The scabs should not be touched or scratched even if they itch, and should be allowed to shed off naturally. Blistered or ulcerated skin can be treated with a prescribed antibiotic ointment or burn treatment cream as per physician's discretion. During the first two days following treatment, care should be taken to prevent trauma to the treated site. Hot baths, massage, etc. should be avoided. The skin should be kept clean to avoid contamination or infection. Any mechanical or thermal damage to the area must be avoided. Moisturizer may be applied only 24 hours after each treatment, and then should be applied regularly throughout the course of the treatment. Make-up may be applied only 24 hours after each treatment if desired, unless an unwanted reaction occurs in the area. Generally, 24 hours after treatment, patients may use regular soaps, but not scrub soaps or exfoliants. The patient should use a high-factor sunscreen (at least 30 SPF) and protect the treated area from sunlight for at least one month after the treatment. Tanning of any sort (sun exposure, tanning beds, and artificial sunless tanning lotions) is not allowed in the treated areas during the entire course of the treatment. Tanning after treatment may cause hyperpigmentation.

The patient should return 1-2 days for skin types I-III or 5-7 days for skin type IV after the test spot treatment to ensure that no adverse events have occurred.

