5.3 PARTICIPANT EXCLUSION CRITERIA

1. Fitzpatrick skin types 5-6.
2. Implantable defibrillators, cardiac pacemakers, and other metal implants
3. Subjects with any implantable metal device in the treatment area
4. Pacemaker or internal defibrillator, or any other active electrical implant anywhere in the body (e.g. cochlear implant).
5. Permanent implant in the treated area, such as metal plates and screws, or an injected chemical substance.
6. Current or history of any kind of cancer, or pre-malignant moles.
7. Severe concurrent conditions, such as cardiac disorders.
8. Pregnancy or intending to become pregnant during the study and nursing.
9. Impaired immune system due to immunosuppressive diseases, such as AIDS and HIV, or use of immunosuppressive medications.
10. History of diseases stimulated by heat, such as recurrent herpes simplex in the treatment area; may be enrolled only following a prophylactic regime.
11. Poorly controlled endocrine disorders, such as diabetes.
12. Any active condition in the treatment area, such as sores, psoriasis, eczema, and rash.
13. History of skin disorders, such as keloids, abnormal wound healing, as well as very dry and fragile skin.
14. History of bleeding coagulopathies, or use of anticoagulants.
15. Use of isotretinoin (Accutane®) within six months prior to treatment.
16. Treating over tattoo or permanent makeup.
17. Excessively tanned skin from sun, tanning beds or tanning creams within the last two weeks.
18. As per the practitioner's discretion, refrain from treating any condition which might make it unsafe for the patient.

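### Section 7.3.1 makes visible erythema part of the test-spot escalation endpoint for every skin type, yet also says erythema may not be visible in darker skin

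*Combined protocol and SAP*

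**What the plan says.** Both statements are in section 7.3.1 (Screening).

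- **Test Spots.** The spot has two listed purposes. The first is to confirm suitability, where the operator must "wait 24-48 hours before assessing the skin response and 5-7 days for skin type IV". The second is to establish the treatment parameters. For this the criterion opens "If the desired endpoint of erythema and edema", qualified as a tip-shaped pattern. If that response "has not been achieved within 10-15 minutes, increase the RF indicator level and perform another test spot" follows. An excessive response leads to lower parameters and a repeat spot.
- **Treatment.** Erythema and edema are again named as the immediate signs of the desired effect. On time course: "The edema usually appears 1-2 minutes after pulsing and reaches its peak (of up to moderate edema) within 30 minutes". On skin type: "erythema is not easily noticeable – if at all – in darker skin types", and then "Therefore, the edema will be more prominent in these patients".

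Section 5.3 excludes "Fitzpatrick skin types 5-6", so the darkest eligible type is IV. The Test Spots text does not vary the 10-15 minute criterion by skin type.

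**The concern.** The escalation rule joins two signs with an *and*. The protocol itself says that one of them may be impossible to see in some patients. For such a patient, failing the criterion may reflect skin colour rather than too weak a response, yet the written consequence is the same: a higher RF level and another spot.

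This matters because the Treatment text tells the operator to adjust the treatment parameters to the test-spot response, so a misread spot can carry through to the full session. Section 2.3.1 lists burns and pigment change among the known risks. The subjects most plausibly affected are those for whom the protocol asks the longest wait after the spot. There is also a consistency cost. An operator who follows the rule literally and one who relies on edema could choose different settings for the same response.

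**Working it through.** The plan gives no figure to reproduce here, and no sample-size or error-rate calculation bears on the point. The check sets the statements side by side, with simple arithmetic on the stated times.

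**1. The erythema component**

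| Element | Test Spots text | Treatment text |
|---|---|---|
| Signs required or expected | Erythema and edema, both | Erythema and edema |
| Skin-type qualifier | None | Erythema may not show in darker skin; edema more prominent |
| Consequence if not met | Raise the level and repeat | Not addressed |

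Take an eligible subject with edema in the tip pattern and no visible erythema, and apply the Test Spots rule as written:

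- edema present: yes
- erythema visible: no
- erythema and edema both present: no
- instruction: increase the level

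Now apply the Treatment text to the same subject. The absence of visible erythema is expected, and edema is the sign to look for. The two readings disagree on whether this subject has responded.

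**2. Who can be affected**

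With types 5-6 excluded, the eligible range ends at type IV. Section 7.3.1 does not say where darker skin begins. If it includes type IV, the conflict falls mainly on that group. The wait before assessing the skin is 5-7 days for type IV, against 24-48 hours for types I-III.

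**3. Whether the time course of edema adds a second conflict**

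Inputs from section 7.3.1: usual onset at 1-2 minutes, peak within 30 minutes, check at 10-15 minutes.

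- Onset to check, shortest: 10 - 2 = 8 minutes. Longest: 15 - 1 = 14 minutes.
- Check to latest stated peak, shortest: 30 - 15 = 15 minutes. Longest: 30 - 10 = 20 minutes.

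Edema should therefore normally be present 8 to 14 minutes before the check. The rule asks whether the response has been achieved, not whether it has peaked, and 30 minutes is an upper bound. The timing produces no contradiction; the conflict lies in the erythema component alone.

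**The case against.** The strongest reply is that section 7.3.1 already contains the answer. A trained operator reads the whole section, including the note that edema is the more prominent sign in darker skin. Sections 8.7 and 12 require protocol and device training. Other text also limits the consequence: parameters come down if the response is excessive, energy is to be set with regard to skin type, the first treatment is to use conservative settings, and the skin is reviewed again a day or more after the spot. On this view the defect is no more than a missing cross-reference.

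Much of this stands. The safeguards make harm less likely, and an experienced operator may well read the rule sensibly. They do not remove the inconsistency. The note on darker skin sits with the instructions for examining the treated area and is not carried into the escalation rule. The step-down provision covers only an excessive response, so it does not stop an adequate one from being escalated. The later skin review takes place after the higher-level spot has been placed.

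Two stronger readings are tempting and should be resisted.

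- A reader might infer that the check comes too early because edema can peak later. The sentence giving the peak also gives the usual onset, which precedes the check.
- A reader might infer that same-visit escalation conflicts with the delayed assessment. Section 7.3.1 lists parameter setting and suitability as separate purposes, each with its own timing, and the delayed review comes after the test spot and before the first full session. It acts as a safeguard.

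**Conclusion.** The concern holds in a narrow form. Section 7.3.1 is internally inconsistent on when the test-spot endpoint has been achieved. Followed literally, its escalation rule can raise the level in a darker-skinned eligible subject who has responded adequately but shows no visible erythema. That conclusion needs only the wording of the section. Placing the problem mainly in type IV rests on the assumption that darker skin includes that type.

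The size cannot be computed:

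- **Number affected.** The documents give neither the expected share of type IV subjects nor how often edema would occur without visible erythema. Enrolment is stated only as maxima (up to 50 and up to 25), so any head count would be invented.
- **Energy increase.** The stated range is 240-280 V and 15-20 ms, but the documents do not say how the RF indicator level maps to voltage or pulse duration, or where a subject would start. A reader might work out an energy multiple across the whole range, or infer that such a subject would be escalated to the top of it. The documents support neither; the step-down rule, patient tolerance and the conservative-settings text all stand in the way.

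This is a matter of safety and consistent conduct. It has no bearing on sample size, power or error rates. It merits correction because a stated rule can misdirect the operator, listed risks are involved, and the change is small.

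**What to change.** The sponsor, with its device experts, and the investigator should reconcile the Test Spots and Treatment texts of section 7.3.1. The escalation rule itself should then state what counts as the endpoint achieved when erythema is not visible, and to which skin types that applies. The same wording should go into the site training under section 8.7. Which signs, settings or read time should govern is a clinical decision for them, and none is proposed here.

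The cost is a short wording amendment, with the ethics review that section 13.2 requires for any amendment, and a training note. No visit, endpoint or analysis changes.

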7.3.2 ENROLLMENT/BASELINE

Enrollment/Baseline Visit (Visit 2, Day 0)

Once a subject has been confirmed that they continue to meet inclusion/exclusion criteria, they will receive a unique identifying number that will be composed of a two-digit site number and a two-digit subject number in sequence. This unique identifier will be used throughout the entire study and will be entered in the subject's case report form (CRF). The investigator will confirm that the subject still meets the inclusion/exclusion criteria. Vital signs and demographics will be collected and a physical exam will be performed. The subject will complete the POSAS.

Photography

Photographs will be taken prior to first treatment and throughout the study according to specified time points detailed in the Schedule of Events Table (section 7.3.7), utilizing standard scientific equipment. Two sets of photographs will be required, one set for the treated side of the body/face and a second set for the untreated side of the body/face.

The photos should be taken in a private room or area of the clinic under controlled conditions, including the distance, angle, background and lighting in order to achieve high-quality sets of photographs. Direct illumination will not be used. The subject should be placed in the same position each time. As each photograph is taken, it should be viewed to ensure that it is in focus and is similar to its baseline counterpart in all technical aspects, including lighting, distance and angle.

For consistency purposes, the same person should ideally take all study photographs, especially per subject. The digital files should follow a consistent standard naming scheme.

Treatment

Subjects will receive treatment as described in section 7.3.1. Only one side of the body/face will be treated. The same side will be treated for the duration of the study. Only half of a scar will be treated

and remaining half will serve as the control. Following treatment, the investigator will examine the treated area and report immediate and short term response. Subjects will complete the 10 cm discomfort/pain VAS immediately after treatment. A new disposal tip will be used for each patient treatment.

Treatment procedure should include positioning of the patient in a manner that enables comfortable access to the treated anatomical site.

Assessment

The investigator will examine the treated areas and report immediate and short term response (30 minutes post-treatment) (pain during treatment, hemorrhage, burn, erythema, edema, purpura) using a 5-point scale: 1=none; 2=trace; 3=moderate; 4=marked; 5=severe.

The assessment of discomfort/pain based on the subject's completion of the 10 cm VAS should also be documented immediately after each treatment.

The normal response to these treatments is transient erythema and edema. If any other side effects occur, as indicated in the protocol, they must be recorded.

Subjects will be discharged from the clinic and will be instructed to return in 2-3 days in order to be examined for adverse events.

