I will conduct the trial in accordance with the clinical investigation plan, Good Clinical Practice guidelines, ISO 14155:2011 (Clinical Investigation of Medical Devices for Human Subjects - Good Clinical Practice), as well as local regulations. I also accept respective revisions to the clinical investigation plan approved by authorized personnel of the Sponsor and by regulatory authorities.

Institution:

[name] [name]

Principal Investigator (Printed name)

Principal Investigator (Signature)

22/2/18

Date

PROTOCOL SUMMARY

TITLE	Clinical Evaluation of the Safety and Performance of Fractional RF for the Treatment of Surgical Scars Following Breast Augmentation, Abdominoplasty or Face Lift
SUMMARY	Split-body/face evaluator-blind study of the safety and performance of fractional RF for the treatment of surgical scars following breast augmentation, abdominoplasty or face lift. The study will enroll up to 50 female subjects requesting treatment of surgical scars following breast augmentation or abdominoplasty and up to 25 male and female subjects requesting treatment of surgical scars following face lift surgery. Subjects will receive a total of three treatments of their surgical scars at one-month intervals on one side of the body or facial incision only. Subjects will be followed up at one, two, three and ten months after their last treatment. Analysis will be performed on all subjects who receive at least one treatment. Outcomes will be compared to the non-treated side.
OBJECTIVES	The objective of this clinical study is to evaluate the safety and performance of fractional RF for the treatment of surgical scars following breast augmentation, abdominoplasty or face lift.

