8.3 TIME PERIOD AND FREQUENCY FOR EVENT ASSESSMENT AND FOLLOW-UP

The occurrence of an AE or SAE may come to the attention of study personnel during study visits and interviews of a study participant presenting for medical care, or upon review by a study monitor. All AEs including local and systemic reactions not meeting the criteria for SAEs will be captured on the appropriate CRF. Information to be collected includes event description, time of onset, clinician's assessment of severity, relationship to investigational device and study procedures (assessed only by those with the training and authority to make a diagnosis), and time of resolution/stabilization of the event. All AEs occurring while on study must be documented appropriately regardless of relationship. All AEs will be followed to adequate resolution.

Any medical condition that is present at the time that the participant is screened will be considered as baseline and not reported as an AE. However, if the study participant's condition deteriorates at any time during the study, it will be recorded as an AE.

Changes in the severity of an AE will be documented to allow an assessment of the duration of the event at each level of severity to be performed. AEs characterized as intermittent require documentation of onset and duration of each episode.

The PI will record all adverse events with start dates occurring any time after informed consent is obtained. At each study visit, the investigator will inquire study subjects about the occurrence of AE/SAEs since the last visit. All adverse events need to be followed until resolution or until study end, whichever occurs first.

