10.6 MEASURES TO MINIMIZE BIAS

10.6.1 ENROLLMENT/ RANDOMIZATION/ MASKING PROCEDURES

At screening, once a subject has signed the informed consent, and inclusion/exclusion criteria has been met, a subject number will be assigned. The subject number will consist of a two-digit code corresponding to the site and a three-digit subject code in numerical sequence. (Example: 10-05 corresponds to site #10, subject #5.)

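### The safety analysis set leaves out subjects exposed to the device only at the test spot, so their reactions are recorded but missing from the adverse event summaries

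*Combined protocol and SAP*

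**What the plan says.** **Exposure.** Section 7.3.1 states: "A small test spot will be performed in a non-conspicuous area of the treatment site, prior to the first complete session". This happens after consent, because the investigator "will obtain an informed consent from the subject prior to any study procedure". The test spot is a tolerance check: "Test spot results will indicate if the patient can tolerate the treatment without developing adverse effects". Subjects come back after it (1-2 days for skin types I-III, 5-7 days for type IV) to be checked for adverse events.

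**Recording.** Section 8.3: "The PI will record all adverse events with start dates occurring any time after informed consent is obtained". Section 7.3.4 repeats the consent start. Section 8.3 also says that a condition present when the participant is screened is "considered as baseline and not reported as an AE", and that later deterioration is an adverse event.

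**Analysis.** The Protocol Summary says "Analysis will be performed on all subjects who receive at least one treatment". Section 10.3 applies one modified intention-to-treat set to performance and safety alike. It requires at least one treatment and a valid performance and safety assessment after baseline. Section 10.4.4 names no other population for its counts of subjects with any adverse event, with a serious one, or withdrawn from treatment because of one.

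**Numbering.** Section 7.3.2, for Visit 2: "Once a subject has been confirmed that they continue to meet inclusion/exclusion criteria, they will receive a unique identifying number". Section 10.6.1, for screening: "once a subject has signed the informed consent, and inclusion/exclusion criteria has been met, a subject number will be assigned".

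**The concern.** The plan has an exposure that comes before the point at which a subject can enter the safety set, and that exposure serves to find out who tolerates the device. A subject who blisters at the test spot and is not taken forward has had the device and a device-related event, but no treatment in the sense of section 10.3.

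Safety is in the study's title and objective, and the number of subjects with a treatment-related adverse event by 10 months is a named safety endpoint. A reader of the final report would take the rate as applying to everyone the device was used on. If some subjects stop at the test spot because of a reaction, the reported rate applies to a group from which those reactors have been removed, and it understates harm among the exposed.

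The two rules on when a subject receives a number, and the schedule's adverse event row, make it less certain that the record of such a subject is complete enough to be analysed.

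**Working it through.** The plan states no adverse event rate, test-spot failure rate or precision target for safety, so there is no figure of its own to reproduce. The check has two parts.

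**1. Is a test spot a treatment for section 10.3?** The term is not defined. The places that bear on it are:

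- Section 7.3.1 describes treatment as a single pass over the area and the test spot as a single pulse.
- Section 7.3.7 has separate rows for the test spot and for administering treatment, the latter marked at Visits 2, 4 and 6.
- Section 10.4.1 places the first treatment at Visit 2 and sets baseline just before it.
- The Protocol Summary counts three treatments in total, which leaves no room for the test spot.
- Against these, one sentence at the end of section 7.3.1 calls the test spot a treatment in passing.

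Four places separate the two and one loose phrase joins them. On the plan's ordinary usage, a test-spot-only subject is outside the safety set. Counting the test spot as a treatment would not settle the matter, because section 10.3 also requires a valid performance assessment after baseline. The first scheduled reviewer rating after treatment is at Visit 8 (Month 3), and an early termination visit takes place only if the subject is willing.

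**2. What does the omission do to the rate?** Let N be the number exposed, k the number stopped after a related test-spot reaction, and p the related event rate among the N − k treated subjects.

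- Reported rate = p
- Rate among all exposed = [k + p(N − k)] / N
- Understatement = k(1 − p) / N

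N = 75 is the maximum enrolment (50 + 25), used here as the number exposed. The values of k and p are assumptions.

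| k | Reported, p = 0 | All exposed, p = 0 | Reported, p = 10% | All exposed, p = 10% |
|---|---|---|---|---|
| 0 | 0/75 | 0/75 = 0% | 10.0% | 10.0% |
| 1 | 0/74 | 1/75 = 1.3% | 10.0% | 11.2% |
| 2 | 0/73 | 2/75 = 2.7% | 10.0% | 12.4% |
| 4 | 0/71 | 4/75 = 5.3% | 10.0% | 14.8% |
| 8 | 0/67 | 8/75 = 10.7% | 10.0% | 19.6% |

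Worked row, k = 4 and p = 10%: (4 + 0.10 × 71)/75 = 11.1/75 = 14.8%, an understatement of 4 × 0.9/75 = 4.8 percentage points.

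With k = 4 and p = 0, the exact (Clopper-Pearson) 95% upper limit for 0/71 is 5.1%. For 4/75 the interval is 1.5% to 13.1%. If 75 were treated and the four came on top of them, the result would be much the same: 4/79 = 5.1%.

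**3. Do the supporting rules agree?** Sections 7.3.2 and 10.6.1 put numbering at different visits. The adverse event row in section 7.3.7, as extracted, is blank at Visit 1 and has ten marks, for Visits 2 to 11. Some rows of that table are displaced: the pain scale appears at Visits 1, 3 and 5, although treatment is at 2, 4 and 6. The adverse event row cannot be displaced in the same way, because moving its ten marks one column to the right would run past the last visit. The concomitant medication row does mark Visit 1.

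**The case against.** The strongest reply is that test-spot harms are well covered. Sections 8.3 and 7.3.4 start recording at consent, section 7.3.1 has a return check, and section 8.1.1 counts procedure-related events as adverse events. Section 7.8 requires any burn in a subject to be reported to the sponsor within 24 hours, without limiting this to treated subjects. All of that stands, and it rules out three stronger readings that a reader might infer.

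- *That the rules remove test-spot events from the record.* They do not: recording runs from consent. The numbering conflict is a contradiction to be resolved, and nothing makes a subject number a precondition for recording an event. The blank Visit 1 cell is weak evidence, since the return check falls in the same window as Visit 2, where adverse event evaluation is marked.
- *That the baseline sentence in section 8.3 excludes them.* It refers to conditions already present at screening. A reaction caused by a pulse given after consent is a new event.
- *That the adverse event rate is estimated only in subjects who tolerated the test spot.* Section 7.3.1 foresees a repeat test spot after an excessive response, so a reactor may still be treated and the event counted. No exclusion criterion names test-spot failure.

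It is also fair to say that the size is unknown and that zero events among treated subjects is an extreme assumption. What the reply does not reach is the analysis set. An event can be fully recorded and promptly reported and still be absent from every summary in section 10.4.4, because its subject is outside the only population defined.

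**Conclusion.** The point holds as a gap in the analysis set. Subjects exposed only to the test spot are left out of the adverse event summaries, both as events and as denominators. The reported rate therefore understates harm among device-exposed subjects if anyone stops at that stage after a reaction.

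This rests on reading the test spot as distinct from treatment, which the plan's usage supports despite one loose phrase. The size cannot be derived from the documents. Under the assumptions shown (75 exposed, up to eight stopped after a related reaction, a rate of 0 or 10% in the rest), the understatement runs from zero to 10.7 percentage points. With four stopped and no related event in the rest, it is 0/71 against 4/75 (5.3%). It is zero if nobody stops.

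The differing numbering times and the adverse event row are inconsistencies that should be tidied. They are not themselves sources of bias.

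**What to change.** - **Sections 10.3 and 10.4.4:** define a safety set of all subjects exposed to at least one device pulse, test spot included. Show test-spot-only subjects and their adverse events on a separate line, so that the treated-only rate can still be read.
- **Sections 7.3.2 and 10.6.1:** reconcile the time of numbering so that every subject has a number before the test spot. Section 10.6.1 puts it at screening but does not mention the test spot, so the order should be stated.
- **Section 7.3.7:** reconcile the adverse event row with the rule in section 8.3 to record from consent, so that the schedule shows evaluation after the test spot.

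None of this alters treatment or clinical management. The cost is wording in these sections, one extra table line and a possibly slightly less favourable adverse event rate.
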